- Diabetic ketoacidosis during study compared with data on DKA events reported by T1D Exchange clinic registry over a 3-month time period
- 3. Number of unanticipated adverse device effects
- 4. Number of other serious device-related adverse events

Secondary Endpoints:

- 1. All device-related adverse events
- 2. CGM hypoglycemia outcomes, compared between the three study time periods
 - a. Overall % time <54 mg/dL
 - b. Overall % time <70 mg/dL
- Times in ranges-overall (70-180 mg/dL, >180 mg/dL, >250 mg/dL, 70-140 mg/dL) compared between the three study time periods
- 4. Mean glucose compared between the three study time periods
- 5. Overall variability (CV and SD) compared between the three study time periods
- 6. Secondary endpoints 2 5 compared during daytime and nighttime, across the three study time periods
- 7. Secondary endpoints 2 5 as well as adverse events, during the study meal challenge periods, for late bolus feature use compared to normal bolus in the meal challenges.
- Time to intervention for hypo- or hyperglycemia during the study meal challenge periods, for late bolus feature use compared to normal bolus in the meal challenges.
- Number of interventions for hypo- or hyperglycemia during the study meal challenge periods for late bolus feature use compared to normal bolus in the meal challenges.
- 10. Subgroup Analysis for all metrics by age cohort, baseline HbA1c cohort, and target activity use (standard target, lower target, sleep activity, exercise activity)

Protocol Overview/Synopsis

After consent is signed, eligibility will be assessed.

Run-In Period:

Participants will return to clinic to undergo device training with the study CGM and a Control-IQ technology 1.5 pump. Training for both devices may be combined, or depending on comfort level of investigator and participant, participants may return for a second session to complete device training and begin the Control-IQ 1.5 run in period. The run-in period will end after 2 weeks of Control-IQ technology 1.5 use.

Participants will have a phone follow up phone call at 1 day, 3 days and 1 week after starting Control-IQ technology 1.5 use, and will return to clinic at two weeks to commence Control-IQ technology 2.0 training.

Treatment Periods:

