516 517 518	 Full bolus for the given carbohydrates and calculated correction, given 45 minutes after starting the meal, based on calculated bolus dose using the bolus calculator (with full amount of carbohydrates entered).
519 520 521	• Full bolus for the given carbohydrates and calculated correction, given 45 minutes after starting the meal, based on calculated bolus dose using the bolus calculator (with full amount of carbohydrates entered) AND enabling the late bolus feature to 45 minutes later.
522	For each meal challenge, participants will:
523 524	1. Be in a fasting state for two hours prior to consuming the last meal of the day, with the last manual insulin bolus more than two hours prior to the meal.

- 525 2. For participants age 6+, only begin the meal challenge if CGM glucose is between 70 mg/dL and 200 mg/dL, and CGM trend arrow is not down.
- For participants age 2-5, only begin the meal challenge if CGM glucose is between 70 mg/dL and 250 mg/dL, and CGM trend arrow is not down.
- 529 Subjects with hyperglycemia > 200mg/dL will reschedule their challenge for another time. If < 530 To mg/dL, carbohydrate treatment can be given, after which the meal challenge can continue.
 - 3. Pediatric participants age 2-5 should have a meal with at least 20 grams of carbohydrates. Participants age 6-13 should have a meal with at least 35 grams of carbohydrates. All other participants should have at least 50 grams of carbohydrates for the study meal challenges. *Each participant should use the same meal for all of their meal challenges in the study. Participants will be encouraged to use the same frozen entrée of their choice for consistency.*
 - 4. Do their best to complete the meal within 30 minutes of starting to eat.
 - 5. Write down the start and end time of eating the meal, as well as the meal content (to include amount of carbohydrate, protein and fat) on the study provided logbook.
 - 6. Bolus for the meal 45 minutes after starting to eat, entering the full carbohydrate amount and using the recommended dose from the bolus calculator. For one of the two challenges during a single treatment period, use the bolus calculator but do not change the bolus time. For the other challenge during the same treatment period, use the bolus calculator but change the bolus time to 45 minutes late.

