2. CGM hypoglycemia outcomes, compared between the three study time periods 922 a. Overall % time <54 mg/dL 923 b. Overall % time <70 mg/dL 924 3. Times in ranges-overall (70-180 mg/dL, >180 mg/dL, >250 mg/dL, 70-140 mg/dL) compared 925 between the three study time periods 926 4. Mean glucose compared between the three study time periods. 927 5. Overall variability (CV and SD) compared between the three study time periods 928 6. Secondary endpoints 2 - 5 compared during daytime and nighttime, across the three study time 929 930 periods 7. Secondary endpoints 2 - 5 as well as adverse events, during the study meal challenge periods, for 931 late bolus feature use compared to normal bolus in the meal challenges. 932 8. Time to intervention for hypo- or hyperglycemia during the study meal challenge periods, for late 933 bolus feature use compared to normal bolus in the meal challenges. 934 935 9. Number of interventions for hypo- or hyperglycemia during the study meal challenge periods for late bolus feature use compared to normal bolus in the meal challenges. 936 10. Subgroup Analysis for all metrics by age cohort, baseline HbA1c cohort (HbA1c at baseline of > 937 7.5%, yes/no), and target activity use (standard target, lower target, sleep activity, exercise 938 939 activity). 940 8.5 Analysis Datasets 941 942 Safety analysis set: All participants who initiate the Treatment Period and use the study device at least one time (including training). 943 CGM analysis set: Any member of the Safety Analysis Set who has at least 24 hours of CGM data during 944 945 either Treatment Period. CGM data occurring within the meal challenge windows (from time of start of meal up to 5 hours afterwards [3 hours for age 2-5]) will not be used to determine whether a subject is 946 included in CGM analysis set or not. 947 948 Late bolus meal challenge set: Any member of the Safety Analysis Set who has at least 24 hours of CGM data during the Treatment Period, and who has at least 3 hours of CGM data for at least one meal 949 challenge. 950 8.6 Analysis of Endpoints 951 8.6.1 Analysis of the Safety Event Endpoints 952 953

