8.6.3 Analysis of CGM Endpoints

CGM metrics will be assessed in CGM analysis set, and computed for the Run-In and both Treatment Periods separately. CGM metrics will be computed per subject over 24 hours, during daytime (6am-11:59pm), and during nighttime (12am-5:59am), as well as by age cohort (adults/adolescents, children 6 – 13, and preschool), baseline HbA1c cohort (HbA1c at baseline of ≥ 7.5%,yes/no), and target activity use as specified by the device (standard target, lower target, sleep activity, and exercise activity). The main statistical comparison will be made between the three 2-week periods (Run In, Treatment

The main statistical comparison will be made between the three 2-week periods (Run In, Treatment Period at standard target, Treatment Period at lower target). The comparison will be pairwise – Run-in vs standard targe, Ru-in vs lower target, and standard vs lower target. The percent time in glycemic ranges will be calculated as the number of measurements in the specified range divided by the total number of measurements for which it can be determined whether or not the measurement was in specified range.

The "Low" and "High" CGM readings will be included in all analyses. Percent time will be compared using a paired t-test assuming sufficient normality assumptions hold, otherwise an appropriate non-parametric method will be utilized.

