8.6.4.1 Late Bolus Meal Challenge Safety and CGM Subgroup Analysis

Two challenges are expected per subjects per treatment period for a total of four challenges, therefore agreement of outcomes will need to be assessed. For continuous outcomes, two sets of Pearson's correlation coefficients will be calculated to measure concordance: one restricted to each treatment period (higher range target and lower range target), and a single coefficient for all four challenges. For categorical outcomes, a Cohen's kappa statistic for agreement or a similarly appropriate statistic will be calculated and presented to describe agreement/dependence of outcomes by individual subjects. Results will be compared by treatment period and across treatment periods.

The analyses described in sections 8.6.1, 8.6.2, and 8.6.3 will be repeated for subjects included in the late bolus meal challenge set. For the CGM outcomes, the mean of the CGM metrics for the two late meal

bolus challenges within study period will be used to account for within-subject non-independence (i.e. one data value per subject per study period).

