8.6.4.2 Time to Intervention Analysis

1005

1006

1007

1018

1031

1032

1033

1039 1040

1041

Time to intervention for both hypo- or hyperglycemia during the study meal challenge periods will be 1008 summarized. Time to intervention is defined as the time (in minutes) from start of meal until the first 1009 treatment is given as defined in Section 6.2. If multiple interventions are needed to treat hypo- or 1010 hyperglycemia during the meal challenge, only time to the earliest intervention will be summarized. The 1011 results will be presented using general summary statistics, as well as utilizing Kaplan-Meier time-to-event 1012 analysis where subjects who complete the meal challenge without requiring any intervention will be right-1013 censored. A cox proportional hazards model will be fit comparing time to intervention between the two 1014 active treatment periods. A p-value from the log-rank test will be used to evaluate whether there is 1015 evidence of a difference between the two target ranges with respect to time to intervention. Results will be 1016 compared by treatment period and across treatment periods. 1017

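### Secondary endpoints 7 to 9 compare the late bolus feature with a normal bolus, but section 8.6.4 specifies no analysis of that contrast

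*Combined protocol and SAP*

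**What the plan says.** **Endpoints.** Secondary endpoints 7 (CGM outcomes and adverse events in the challenges), 8 (time to intervention) and 9 (number of interventions) are each defined, in the synopsis and again in section 8.4, "for late bolus feature use compared to normal bolus in the meal challenges".

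**Design.** Each two-week treatment period contains two challenges, with the bolus given 45 minutes after the start of the meal in both. Section 5.1.1, step 6, separates them: "For one of the two challenges during a single treatment period, use the bolus calculator but do not change the bolus time". In the other challenge the bolus time is changed to 45 minutes late.

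**Analysis.**
- Section 8.6.4.1 repeats the analyses of 8.6.1 to 8.6.3 in the challenge set. For CGM outcomes, the mean over the two late-meal "bolus challenges within study period will be used to account for within-subject non-independence (i.e. one data value per subject per study period"). The statistic it names for separate challenge values of a continuous outcome is Pearson's: "correlation coefficients will be calculated to measure concordance: one restricted to each treatment period (higher range target and lower range target"), plus one coefficient over all four challenges. Categorical outcomes get a kappa or similar agreement statistic.
- The CGM comparisons carried over from 8.6.3 are "Run-in vs standard targe, Ru-in vs lower target, and standard vs lower target".
- In 8.6.4.2 the Cox model compares the two active treatment periods, and the log-rank test looks for "evidence of a difference between the two target ranges with respect to time to intervention".
- Section 8.6.4.3 gives summary statistics, overall and by type of intervention, compared by and across treatment periods.

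**The concern.** Section 8.6.4 mentions neither use of the late bolus feature nor the normal bolus as something to be compared. The factor it does use is treatment period, which means glucose target. Followed as written, the plan produces a target comparison for challenge CGM metrics and for time to intervention, but no specified estimate of what the feature does. For CGM metrics the averaging rule also removes the contrast from the analysed values. The endpoints are exploratory and the challenge-level data remain in the logbook and eCRF, so nothing is lost for good. What is at stake is that the method for a contrast named in three secondary endpoints would be chosen after the data are seen.

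**Working it through.** The plan gives no power or precision figure for the challenges (section 8.3 says that the sample size does not rest on statistical principles), so there is no stated figure to reproduce.

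**1. Endpoint against analysis**

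| Endpoint | Contrast in 8.4 | Comparison in 8.6.4 |
|---|---|---|
| 7, CGM | feature vs normal bolus | mean of both challenges, compared between study periods |
| 7, adverse events | feature vs normal bolus | 8.6.1 and 8.6.2 repeated, by study period |
| 8 | feature vs normal bolus | Cox and log-rank between target periods |
| 9 | feature vs normal bolus | summaries by and across treatment periods |

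**2. What the CGM averaging estimates.** Let N_t be the normal-bolus mean at target t (S standard, L lower) and D_t the feature effect there. With all challenges usable:

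- period mean = (N_t + N_t + D_t)/2 = N_t + D_t/2
- lower minus standard = (N_L − N_S) + (D_L − D_S)/2

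If the feature effect is the same at both targets, it cancels. If D_S = 10 and D_L = 5, the target contrast contains (5 − 10)/2 = −2.5, while the average feature effect is (10 + 5)/2 = 7.5. A Pearson coefficient does not change when a constant is added to one of its two variables, so the within-period correlations cannot show the effect either.

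**3. Illustration.** Assumed: 72 participants, 2 targets, 2 bolus types, between-participant SD 10, residual SD 8, target effect 3.

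| Feature effect added | Target contrast (planned) | Within-period Pearson r | Feature minus normal |
|---|---|---|---|
| 0 | 1.65 (p = 0.085) | 0.50, 0.58 | −1.3 |
| −10 | 1.65 (p = 0.085) | 0.50, 0.58 | −11.3 |
| −30 | 1.65 (p = 0.085) | 0.50, 0.58 | −31.3 |

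**4. Incomplete challenges.** The challenge set in section 8.5 admits anyone with enough CGM data overall "and who has at least 3 hours of CGM data for at least one meal" challenge. If a share m lacks the feature challenge at one target only, that period mean shifts by m × D/2. For m = 0.10 this is 0.05 × D, and for m = 0.20 it is 0.10 × D. Both shares are assumptions. This is a side effect on the target contrast, not a measure of the missing analysis.

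**5. What the direct contrast could deliver.** The minimum number of completers is 30 + 30 + 12 = 72. With no missed challenges, that gives 72 × 4 = 288 challenges, 144 of each kind. Let sigma be the within-participant SD of one challenge value. One feature-minus-normal difference has variance 2 × sigma². The average over two targets has variance 2 × sigma²/2 = sigma², so SE = sigma/√72 = 0.118 sigma. A two-sided 5% paired t-test at an assumed 80% power detects:

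- n = 72: 0.335 sigma
- n = 30: 0.529 sigma
- n = 12: 0.889 sigma

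(The normal approximation gives 0.33, 0.51 and 0.81.) The documents do not give sigma. If it is 15 to 25 points for time in range, then 0.335 × 15 = 5.0 and 0.335 × 25 = 8.4 points overall. This assumes that the feature effect does not vary between participants; any such variation makes these figures optimistic.

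**6. Run-in comparisons.** The schedule places challenges only in the Control-IQ 2.0 periods. Two of the three comparisons carried over from 8.6.3 (run-in vs standard, run-in vs lower) therefore have no challenge data.

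**7. What counts as an intervention.** Section 8.6.4.2 times the first "treatment is given as defined in Section 6.2", which is the adverse-event section. The treatments a participant may take during a challenge are in 5.1.1, steps 7 and 8, and 8.6.4.3 groups carbohydrate treatments in 10-gram increments. As written, endpoints 8 and 9 may count different events.

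**The case against.** The best reply is that sections 8.1 and 8.4 together already specify something. Section 8.4 names the contrast, and 8.1 says that correlated data from one subject under several conditions will be accounted for, giving a paired t-test as the example for continuous outcomes. A non-parametric fallback and differences in proportions are also there. In addition, comparison by treatment period could mean within each period, where the two challenges differ in bolus type. Section 8.2 states no formal hypotheses and keeps p-values out of formal inference.

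Part of this stands. The contrast is prespecified; what is left open is strictly the method. The stakes are modest. The empty run-in comparisons cannot produce a wrong result. The Section 6.2 reference may be a slip, and 8.6.4.3 has the Medical Monitor define counting logic before analysis.

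The rest does not cure the gap. The paired t-test in 8.1 is a generic example, and the specific averaging rule in 8.6.4.1 overrides it for challenge CGM values. Section 8.1 supplies no factor for a time-to-event model, and 8.6.4.2 names a different one. The wording about treatment periods never mentions bolus type.

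**Conclusion.** The concern holds. Following 8.6.4 as written answers a question about glucose target, while endpoints 7 to 9 ask about the late bolus feature. For CGM metrics the planned value carries no information on a feature effect that is equal at both targets, and only half the difference between the two effects otherwise; this follows from the algebra and needs no assumed figures. For time to intervention the stated factor is the wrong one for endpoint 8, and for number of interventions and adverse events no split by bolus type is specified. The detectable differences depend on 72 completers, no missed challenges, 80% power, no variation of the effect between participants and, in points, an assumed sigma. Because the endpoints are exploratory and the data recoverable, this should be fixed but does not threaten the primary safety objective.

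**What to change.** - **CGM metrics (8.6.4.1).** Keep one value per challenge. Take each participant's feature-minus-normal difference within each target period, average over the two targets, and analyse it as paired data. A mixed model is a similar but not identical alternative: bolus type, target, their interaction, period and challenge order as fixed effects, participant as random. Its period term goes beyond the no-period-effect assumption in 8.1, so say why it is included.
- **Challenge order.** The documents do not say that order within a period is randomised. Take it from the logbook. If nearly everyone uses the same order, report that order and bolus type cannot be separated.
- **Time to intervention (8.6.4.2).** Make bolus type the Cox factor, with robust errors clustered on participant, and keep the target comparison as an additional analysis. A participant-stratified model would lose those with no intervention: at an assumed probability of 10%, 20% or 30% per challenge, independent over four challenges, (1 − p)⁴ = 66%, 41% or 24%, or about 47, 30 or 17 of 72.
- **Number of interventions and adverse events.** Tabulate by bolus type.
- **Tidying.** Remove the run-in comparisons for challenge data. Reconcile the Section 6.2 reference with 5.1.1, steps 7 and 8, and 8.6.4.3, so that endpoints 8 and 9 count the same events.

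The cost is SAP rewording and a little more programming. Participants, challenges and data collection stay the same.

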8.6.4.2 Time to Intervention Analysis

1005

1006

1007

1018

1031

1032

1033

1039 1040

1041

Time to intervention for both hypo- or hyperglycemia during the study meal challenge periods will be 1008 summarized. Time to intervention is defined as the time (in minutes) from start of meal until the first 1009 treatment is given as defined in Section 6.2. If multiple interventions are needed to treat hypo- or 1010 hyperglycemia during the meal challenge, only time to the earliest intervention will be summarized. The 1011 results will be presented using general summary statistics, as well as utilizing Kaplan-Meier time-to-event 1012 analysis where subjects who complete the meal challenge without requiring any intervention will be right-1013 censored. A cox proportional hazards model will be fit comparing time to intervention between the two 1014 active treatment periods. A p-value from the log-rank test will be used to evaluate whether there is 1015 evidence of a difference between the two target ranges with respect to time to intervention. Results will be 1016 compared by treatment period and across treatment periods. 1017

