1.3.1.3 Hypoglycemia

- As with any person having type 1 diabetes and using insulin, there is always a risk of having 59
- hypoglycemia. The frequency of hypoglycemia should be no more and possibly less than it would be 60
- as part of daily living. Symptoms of hypoglycemia can include sweating, jitteriness, and not feeling well. 61
- There is the possibility of fainting or seizures (convulsions) and that for a few days the participant may 62
- not be as aware of symptoms of hypoglycemia. A CGM functioning poorly and significantly over-63
- reading glucose values could lead to inappropriate insulin delivery. The study meal challenges, requiring 64
- boluses to be delivered late, could increase the risk of hypoglycemia. 65

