1.3.1.4 Risk of Hyperglycemia

- Hyperglycemia and ketonemia could occur if insulin delivery is attenuated or suspended for an 67
- extended period or if the pump or infusion set is not working properly. A CGM functioning poorly 68
- and significantly under-reading glucose values could lead to inappropriate suspension of insulin delivery. 69
- 70 The study meal challenges, requiring boluses to be delivered late, could increase the risk of
- hyperglycemia. 71

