 - 7. Not give an additional bolus during 5 hours (3 hours for participants age 2-5) after the start of meal challenge (i.e., after start of meal), unless BG is above 300 mg/dL for more than 1 hour, or symptoms of hyperglycemia develop.
 - 8. Not take additional carbohydrates during 5 hours (3 hours for participants age 2-5) after the start of meal challenge (i.e., after start of meal), unless BG is < 70 mg/dL, or symptoms of hypoglycemia develop.
 - 9. Not exercise for 5 hours (3 hours for participants age 2-5) after the meal challenge begins.
- 551 10. Make sure sleep activity is not active for the 5 hours (3 hours for participants age 2-5) after the meal challenge begins (start of meal).
 - 11. Notify the site within 24 hours after completion of each meal challenge.

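### Time to intervention in the meal challenges merges treatment of lows with treatment of highs, so opposite shifts between the two targets can offset within this one exploratory endpoint

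*Combined protocol and SAP*

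**What the plan says.** Section 8.6.4.2 opens by saying "Time to intervention for both hypo- or hyperglycemia during the study meal challenge periods will be" summarized. The event is the first time "treatment is given as defined in Section 6.2", counted in minutes from the start of the meal. Where a challenge needs several treatments, "only time to the earliest intervention will be summarized". Censoring is for the opposite case: "subjects who complete the meal challenge without requiring any intervention will be" right-censored. One Cox model compares the two active treatment periods, and one log-rank p-value is used to look for "evidence of a difference between the two target ranges with respect to time to intervention". The section plans no separate time to carbohydrate or time to added insulin, and no handling of one as a competing event for the other.

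Section 5.1.1 shows that the two treatments are opposite and are triggered differently. Step 7 allows an extra bolus only when BG has been above 300 mg/dL for more than 1 hour, or with symptoms of hyperglycemia. Step 8 rules out extra carbohydrate "unless BG is < 70 mg/dL, or symptoms of hypoglycemia develop". Observation lasts 5 hours from meal start, or 3 hours at age 2-5 (Section 8.6.4).

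Secondary endpoint 8 in Section 8.4 uses the same pooled wording but names a different contrast: late bolus feature against normal bolus.

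**The concern.** A single hazard ratio for the first treatment of either kind is the ratio of two summed hazards. If one condition produces more lows and fewer highs, the sum can stay nearly constant while both parts change. The contrast actually tested in Section 8.6.4.2 is a 90-130 against a 112.5-160 mg/dL target, where such a trade is plausible. A flat Kaplan-Meier comparison could then be read as no difference in the need for rescue, when the kind of rescue had changed. The first-event rule also discards a later treatment of the other kind in the same challenge.

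The risk sections treat the two directions as distinct hazards of the challenges. Section 1.3.1.3 says the challenges, requiring "boluses to be delivered late, could increase the risk of hypoglycemia", and Section 1.3.1.4 says "The study meal challenges, requiring boluses to be delivered late, could increase the risk of" hyperglycemia. That supports reporting two outcomes. It does not itself show a trade between them.

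**Working it through.** **Is it one event or two?** The opening phrase of Section 8.6.4.2 could be read as two summaries. The operative rules fit only one: the clock stops at the first treatment, only the earliest counts, and only challenges with no treatment at all are censored. Two separate analyses would need a rule for a challenge that had the other treatment first, and there is none.

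**Inputs from the documents.** At least 72 completers (30 + 30 + 12; synopsis and Section 8.3); 2 challenges per period, 4 in total (Section 8.6.4.1); two-sided 5% testing (Section 8.16); window 300 minutes, or 180 minutes for the 12 youngest. Section 8.3 says the sample size has no statistical basis, so there is no planned figure to reproduce.

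**Number of challenges.** 72 × 4 = 288, so 144 per target if every completer does all four.

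**Assumptions.** The documents give no intervention rates, so the risks below are assumed. Each is the risk of that treatment over 300 minutes if the other did not occur. Times are exponential, so the hazard over the window is −ln(1 − p). Challenges are treated as independent. Windows are 300 minutes for 60/72 of challenges and 180 minutes for 12/72.

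**Composite hazard ratio** (lower against standard target) = sum of the two hazards under the lower target ÷ sum under the standard target.

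- Exact offset (lows 10% to 20%, highs 20% to 10%): (0.2231 + 0.1054) ÷ (0.1054 + 0.2231) = 1.00. The component ratios are 0.2231 ÷ 0.1054 = 2.12 and 0.1054 ÷ 0.2231 = 0.47. The intervention-free share at 300 minutes is 0.9 × 0.8 = 0.72 under both targets.
- Partial offset (highs 20% to 15%): (0.2231 + 0.1625) ÷ (0.1054 + 0.2231) = 1.17.
- Rare highs (lows 20% to 40%, highs 5% to 2%): (0.5108 + 0.0202) ÷ (0.2231 + 0.0513) = 1.93.

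**Rejection rates.** Simulated log-rank tests, 4,000 runs per row, 144 challenges per target. The component tests are cause-specific: a first treatment of the other kind ends follow-up.

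| Lows | Highs | Composite HR | Composite rejects | Lows alone | Highs alone |
|---|---|---|---|---|---|
| 10% to 20% | 20% to 10% | 1.00 | 5% | 61% | 59% |
| 5% to 15% | 15% to 5% | 1.00 | 5% | 77% | 78% |
| 15% to 30% | 30% to 15% | 1.00 | 5% | 81% | 80% |
| 10% to 20% | 20% to 15% | 1.17 | 11% | 60% | 18% |
| 10% to 20% | 20% to 20% | 1.36 | 29% | 59% | 5% |
| 20% to 40% | 5% to 2% | 1.93 | 87% | 95% | 20% |

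With 72 challenges per group, the first row becomes 5% against 35% for each component.

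The first three rows were chosen to cancel exactly and show the worst case. The fifth shows that pooling costs power for lows even when highs do not move. The last shows that it costs little when treated highs are rare.

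**The case against.** The strongest reply is that the trial does not depend on this endpoint to see direction. Secondary endpoint 7 reports CGM time below 54 and 70 and above 180 and 250 mg/dL, plus adverse events, within the challenge windows, and Section 8.6.4.1 repeats the safety and CGM analyses there. Section 8.6.4.3 summarizes intervention counts by type and lets the categories grow with what is observed. Section 8.2 states no formal hypotheses and keeps p-values out of formal inference. Any-rescue-free time is also a legitimate summary of burden.

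Most of this stands. A reader might infer that a harm would go unseen in the trial as a whole, or that the trial could not say whether the late bolus feature is safer. The documents do not support that, because the CGM outcomes keep direction.

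The cover has gaps:

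- Section 8.6.4.1 averages the two challenges within a period. One used the late bolus setting and one did not (Section 5.1.1), so that average serves the target contrast but does not isolate the feature.
- A low is a reportable adverse event only if severe, or if it led to facility care or site guidance (Section 6.2.3), unless linked to an adverse device effect or device discontinuation (Section 6.2.2). Other self-treated lows in a challenge do not appear there.
- The types listed for the counts are timing and carbohydrate amount. A low/high split is possible but not committed.

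Two further objections limit the evidence. The rates are assumed, and highs that meet the trigger may be uncommon within 5 hours. Sections 1.3.1.3 and 1.3.1.4 describe risks shared by all challenges, since every challenge bolus is given 45 minutes after the meal starts. The case for opposite shifts rests on the plausibility of the target contrast, not on those sections.

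**Conclusion.** The point holds for this endpoint. As written, Section 8.6.4.2 cannot separate a change in treated lows from a change in treated highs. Under the assumed rates its log-rank test rejects in 5% of runs with exact offset and 11% with partial offset, where a lows-only analysis rejects in about 60% or more. The loss falls to 87% against 95% when highs are rare.

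These figures rest on assumed risks, constant hazards, full completion and independent challenges. Real challenges repeat within participants, and the glucose trigger for highs cannot be met until BG has been above 300 mg/dL for over an hour, so the exact cancellation is illustrative. The consequence is misreading one exploratory secondary endpoint, not failure of a formal test. Severity is minor.

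**What to change.** In Section 8.6.4.2:

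- Report time to first hypoglycemia treatment and time to first hyperglycemia treatment separately, each with the other as a competing event: cumulative incidence curves and a cause-specific hazard ratio with 95% confidence interval.
- Do this for the target contrast and for the late-bolus against normal-bolus contrast named in secondary endpoint 8.
- Keep the combined time to first intervention as a descriptive summary.
- State directly what record counts as each kind of intervention. The present pointer is to Section 6.2, which covers adverse events and does not define treatments given in a challenge.

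In Section 8.6.4.3, commit to splitting the intervention counts into those for lows and those for highs.

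The cost is SAP wording and a few extra tables from data already planned for these endpoints. Each component has fewer events than the composite, so its interval will be wider. This is a cheap improvement.
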